## **Study Protocol**

This project aims to evaluate safety and security of patients submitted to minimally invasive radical prostatectomy, who received discharge from hospital in the same day of the surgery (Group I), on the 1st post-surgery day (Group II) and in the 2nd post-surgery day (Group III – control). The specific aims are the evaluation of fail index and factors that influence the permanence in the hospital, the satisfaction of patients, the perception of security of patient, the index of post-discharge complications and the costs related to different times of hospitalization. On randomization, those patients in Group I must match the early hospital discharge criteria defined in the study. Thus, they will be forwarded to "Casa de Apoio Madre Paulina", where will receive nursing care until the next day when, in the morning, will be reevaluated in the ambulatory of urology from Barretos Cancer Hospital. The patients of Group II will be evaluated in the ambulatory in the 2nd postsurgery day, before the discharge. In the Group III (control), the patients will be discharged in the 2nd post-surgery day (routine of Barretos Cancer Hospital). All patients who accept to be enrolled in the study will sign the Consent Term previously the surgery. At the 10th post-surgery day, in the follow-up, it will be applied the questionnaire SATISBR and an inventory.

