## Statistical Analysis Plan

This project aims to evaluate safety and security of patients submitted to minimally invasive radical prostatectomy, who received discharge from hospital in the same day of the surgery (Group I), on the 1st post-surgery day (Group II) and in the 2nd post-surgery day (Group III – control). The specific aims are the evaluation of fail index and factors that influence the permanence in the hospital, the satisfaction of patients, the perception of security of patient, the index of post-discharge complications and the costs related to different times of hospitalization. On randomization, those patients in Group I must match the early hospital discharge criteria defined in the study. Thus, they will be forwarded to "Casa de Apoio Madre Paulina", where will receive nursing care until the next day when, in the morning, will be reevaluated in the ambulatory of urology from Barretos Cancer Hospital. The patients of Group II will be evaluated in the ambulatory in the 2nd postsurgery day,

before the discharge. In the Group III (control), the patients will be discharged in the 2nd post-surgery day (routine of Barretos Cancer Hospital). All patients who accept to be enrolled in the study will sign the Consent Term previously the surgery. At the 10th post-surgery day, in the follow-up, it will be applied the questionnaire SATISBR and an inventory. The data will be descriptive considering average, standard deviation, minimum and maximum value and quartile to the quantitative variables and frequency tables to the qualitative variables. In order to determine the groups' homogeneity, some sociodemographic and clinical characteristics will be compared. To the qualitative variables, it will be used chi-squared test (of Fishers exact test), and to the quantitative variables it will be used variance analysis (or Kruskal-Wallis test). The patients' satisfaction will be measured using SATIS-BR, which consists in three numeric domains (ranging from 1 to 5). The comparison of each domain among the groups will be performed using ANOVA. Then, linear regression will be performed in order to analyze the relationship of the patients' characteristics influencing the satisfaction. The rates of fail, clinical security, security perception and post-discharge complications will be compared among the groups using chi-squared test (of Fisher's exact test). There will be considered the significance level of 5%.

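### Post-discharge complications are counted over a different window in each group, because discharge day is the randomised factor; separately, the analysis set is not stated

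*Combined protocol and SAP*

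**What the plan says.** The Study Protocol section and the Statistical Analysis Plan section share the same design text.

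- **Groups.** They are set apart by discharge day: "who received discharge from hospital in the same day of the surgery (Group I"), "on the 1st post-surgery day (Group II"), and day 2 in Group III, the control.
- **Group II timing.** The same paragraph also says: "The patients of Group II will be evaluated in the ambulatory in the 2nd postsurgery day, before the discharge". Read literally, this places the discharge no earlier than day 2.
- **Comparison.** The SAP says: "The rates of fail, clinical security, security perception and post-discharge complications will be compared among the groups", using a chi-squared or Fisher's exact test at the 5% level. It gives no opening or closing day for the complication count.
- **Follow-up.** One visit is common to all groups: "At the 10th post-surgery day, in the follow-up, it will be applied the questionnaire SATISBR and an inventory".
- **Criteria.** "On randomization, those patients in Group I must match the early hospital discharge criteria defined in the study". The next sentence starts "Thus, they will be forwarded to" and names the support house. No such requirement is stated for Groups II or III.
- **Analysis set.** Neither section says which patients enter the comparisons, or how a Group I patient who misses the criteria is handled. Failure is part of the first specific aim, "The specific aims are the evaluation of fail index and factors that influence the permanence in the hospital", but it is not defined.

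**The concern.** An outcome that can be counted only after discharge starts its clock at an event that the trial itself assigns. A complication on the evening of surgery or on day 1 is countable in a Group I patient who has left hospital. The same complication in a Group III patient, still in hospital, is not. This happens even if every patient is discharged on the planned day and analysed as allocated. Randomisation balances the patients, but it does not balance the time over which they are observed. The distortion runs against same-day discharge, the arm whose safety is in question. It could produce a false signal of harm or mask a true benefit.

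The second matter is separate and conditional. The criteria are applied to one arm only and the analysis set is unstated, so two analysts could use different denominators for Group I. If one of them excluded patients who missed the criteria, the remaining Group I would be a selected group, and the comparison would tilt in its favour.

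**Working it through.** The documents give no event rate, sample size or power calculation, so there is no planned figure to reproduce. The group structure, discharge days, test and 5% level come from the documents. All other inputs below are assumptions.

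**1. Counting window**

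Assumptions: no true effect; total complication risk 0.10 in every group; 100 patients per group; all analysed as allocated; counting closes on the same day after surgery in all groups. A share *s* of events falls between day 0 and day 2, split evenly over the two intervals.

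Countable rates:

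- Group I: 0.10
- Group II from day 1: 0.10 × (1 − s/2); from day 2: 0.10 × (1 − s)
- Group III: 0.10 × (1 − s)

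Rejection rates are for the Pearson chi-squared test with 2 degrees of freedom at 5%, simulated with 200,000 trials per case:

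| Early share *s* | Group II starts | Countable rates I / II / III | Rejection |
|---|---|---|---|
| 0.2 | day 1 | 10% / 9% / 8% | 6.6% |
| 0.2 | day 2 | 10% / 8% / 8% | 7.4% |
| 0.4 | day 1 | 10% / 8% / 6% | 13.4% |
| 0.4 | day 2 | 10% / 6% / 6% | 17.5% |
| any, common window | – | 10% / 10% / 10% | 4.9% |

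The built-in difference between Groups I and III is 0.10 × s, that is 2 points at s = 0.2 and 4 points at s = 0.4, with Group I higher. It does not shrink with sample size, so the false rejection rate grows. At s = 0.4 with Group II on day 1 it is about 9% with 50 per group and about 24% with 200.

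**2. Criteria and analysis set**

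Three readings of the text are possible.

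- The criteria gate the transfer to the support house and every patient is kept as allocated: bias 0.
- All patients are screened against the criteria before allocation: bias 0.
- Group I patients who miss the criteria are dropped from the comparison.

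On the third reading, let *f* be the share missing the criteria and RR their relative risk, with overall risk 0.10. The risk in the analysed Group I is 0.10 / ((1 − f) + f × RR), against 0.10 in Groups II and III.

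- f = 0.1, RR = 2: 0.10 / 1.1 = 0.0909, difference −0.9 points, rejection 5.3% with 100 allocated per group.
- f = 0.2, RR = 3: 0.10 / 1.4 = 0.0714, difference −2.9 points, rejection 8.5%.
- f = 0.3, RR = 3: 0.10 / 1.6 = 0.0625, difference −3.75 points, rejection 10.4%.

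**3. Both together**

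The window effect raises the Group I rate relative to the others, and dropping patients lowers it. With 100 per group and Group II on day 1:

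- f = 0.2, RR = 3: rejection is 6.0% at s = 0.2 and 6.9% at s = 0.4, below the 8.5% from selection alone.
- f = 0.3, RR = 3: rejection is about 7.2% at either *s*, below 10.4%.

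The two effects partly cancel, so their rejection rates cannot be summed.

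**The case against.** A reader might infer that the trial compares a selected Group I with unselected Groups II and III. The documents do not support that. The criteria sentence leads directly into the transfer to the support house, which reads as a gate on discharge. A fail rate in Group I makes sense only if patients not discharged as planned stay in the denominator. No sentence says that anyone is dropped, replaced or moved. Describing the groups by the discharge received is weak evidence for as-treated grouping, because the phrase sits in a general statement of aims. The words about randomisation could also mean screening of all patients before allocation, although the sentence names Group I only. This part of the objection stands: what remains is silence on the analysis set for outcomes other than fail, not evidence of selection.

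It can also be said that every rate used here is assumed and that the effects are modest in small groups. That stands too. The window problem, however, does not depend on the size of the illustration. It follows from the named endpoint and the randomised discharge days, and it vanishes only if no complications occur before day 2.

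The planned tests of group homogeneity do not help with either matter. They cover only some characteristics, and comparing patient characteristics cannot detect unequal counting windows.

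**Conclusion.** The point holds for the counting window. Followed exactly, the plan compares complication counts that open on different days by design, to the disadvantage of same-day discharge. Under the assumed 10% total risk and 100 per group, false rejection is about 6.6% to 17.5%, depending on the early share (20% or 40%) and on the unresolved Group II day, against 4.9% with a common window. The true size is unknown.

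On the analysis set the point is only that a statement is missing. Bias is zero if all are kept as allocated, which the text favours, or if all are screened before allocation. It would favour Group I only if patients who miss the criteria were dropped. This should be fixed, on the strength of the unequal windows and the missing statement rather than of the simulated rates. Confidence is medium.

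**What to change.** 1. Make the between-group comparison of complications a count from surgery to a common day in all three groups, for example the day-10 visit already planned. Keep the post-discharge count as descriptive.
2. State in the SAP that every between-group comparison uses all randomised patients in their allocated group, and that a Group I patient who misses the early-discharge criteria stays in Group I and counts as a fail.
3. Reconcile the passages on Group II: discharge on the first day after surgery against an evaluation on the second day that precedes discharge. Until this is settled, neither its counting window nor a fail in that group can be defined.

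The cost is the recording of in-hospital complications in all groups, plus some wording in the protocol and SAP. The changes may move the result in either direction: the first may make Group I look better, and the second may make it look worse. Recording the criteria checklist in Groups II and III as well is optional and not part of the fix.

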## Statistical Analysis Plan

This project aims to evaluate safety and security of patients submitted to minimally invasive radical prostatectomy, who received discharge from hospital in the same day of the surgery (Group I), on the 1st post-surgery day (Group II) and in the 2nd post-surgery day (Group III – control). The specific aims are the evaluation of fail index and factors that influence the permanence in the hospital, the satisfaction of patients, the perception of security of patient, the index of post-discharge complications and the costs related to different times of hospitalization. On randomization, those patients in Group I must match the early hospital discharge criteria defined in the study. Thus, they will be forwarded to "Casa de Apoio Madre Paulina", where will receive nursing care until the next day when, in the morning, will be reevaluated in the ambulatory of urology from Barretos Cancer Hospital. The patients of Group II will be evaluated in the ambulatory in the 2nd postsurgery day,

before the discharge. In the Group III (control), the patients will be discharged in the 2nd post-surgery day (routine of Barretos Cancer Hospital). All patients who accept to be enrolled in the study will sign the Consent Term previously the surgery. At the 10th post-surgery day, in the follow-up, it will be applied the questionnaire SATISBR and an inventory. The data will be descriptive considering average, standard deviation, minimum and maximum value and quartile to the quantitative variables and frequency tables to the qualitative variables. In order to determine the groups' homogeneity, some sociodemographic and clinical characteristics will be compared. To the qualitative variables, it will be used chi-squared test (of Fishers exact test), and to the quantitative variables it will be used variance analysis (or Kruskal-Wallis test). The patients' satisfaction will be measured using SATIS-BR, which consists in three numeric domains (ranging from 1 to 5). The comparison of each domain among the groups will be performed using ANOVA. Then, linear regression will be performed in order to analyze the relationship of the patients' characteristics influencing the satisfaction. The rates of fail, clinical security, security perception and post-discharge complications will be compared among the groups using chi-squared test (of Fisher's exact test). There will be considered the significance level of 5%.

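### SATIS-BR satisfaction is tested only with a three-group ANOVA; no difference from the control group, with its confidence interval, is planned

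*Combined protocol and SAP*

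**What the plan says.** Satisfaction is one of the specific aims in both sections; the Study Protocol section lists "the satisfaction of patients, the perception of security of patient" among them. It is not ranked as primary or secondary. The control arm is explicit: "In the Group III (control), the patients will be discharged in the 2nd post-surgery day (routine of Barretos Cancer Hospital"). SATIS-BR is given on the 10th post-surgery day and yields three numeric domain scores, each from 1 to 5.

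The Statistical Analysis Plan then provides three things that bear on satisfaction:

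- Descriptive statistics: "The data will be descriptive considering average, standard deviation, minimum and maximum value and quartile to the quantitative variables". It does not say that these will be tabulated by group.
- The group comparison: "The comparison of each domain among the groups will be performed using ANOVA".
- A further model: "Then, linear regression will be performed in order to analyze the relationship of" patients' characteristics to satisfaction. It does not say whether discharge group is a term.

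One 5% significance level is stated for all analyses. Neither section names a contrast with Group III, a post-hoc procedure, a between-group mean difference or a confidence interval. The Study Protocol section contains no analysis methods.

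**The concern.** Naming routine day-2 discharge as control implies two comparisons: same-day discharge against routine, and day-1 discharge against routine. For each, a reader will want to know how far satisfaction shifts on the 1-to-5 scale and how precisely that shift is known. The omnibus F-test asks only whether the three means are all equal.

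Two misreadings become possible. A significant F does not show which early-discharge group departs from control, or whether its patients were more or less satisfied. A non-significant F may be taken to mean that patients were equally satisfied when the data still allow a sizeable loss. If the contrasts are left to be chosen after an F-test, the choice of comparisons and of any adjustment is also made with the data in hand.

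**Working it through.** The plan states no sample size, SD, target difference or power, so it has no figure to reproduce. From the plan come the three groups, the control (Group III), the three domains scored 1 to 5, the ANOVA and the 5% level. Everything else below is assumed: equal arms of n, a common SD, and the pooled ANOVA variance on 3n − 3 degrees of freedom.

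**Same F, opposite answers.** Take n = 50 and SD = 0.5. For means of 4.5, 4.5 and 4.2 the grand mean is 4.4 and the squared deviations sum to 0.01 + 0.01 + 0.04 = 0.06. Then F = (50 × 0.06 / 2) / 0.25 = 6.00 on 2 and 147 df, p = 0.003. Permuting the means leaves F unchanged:

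| Means (I, II, III) | F, p | I-III | II-III |
|---|---|---|---|
| 4.5, 4.5, 4.2 | 6.00, 0.003 | +0.30 | +0.30 |
| 4.2, 4.5, 4.5 | 6.00, 0.003 | −0.30 | 0.00 |
| 4.5, 4.2, 4.5 | 6.00, 0.003 | 0.00 | −0.30 |

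The unadjusted 95% half-width for each difference is 1.976 × 0.5 × √(2/50) = 0.20 points.

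**What a null result leaves open.** The half-width in SD units is t(0.975; 3n − 3) × √(2/n):

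- n = 15: 2.018 × 0.365 = 0.74
- n = 30: 1.988 × 0.258 = 0.51
- n = 50: 1.976 × 0.200 = 0.40

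At n = 30 this is 0.513 × SD, or ±0.26, ±0.41 and ±0.51 points for an SD of 0.5, 0.8 and 1.0. These limits apply even when the observed I-III difference is exactly zero.

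**F-test against control contrasts at n = 30.** The two-sided 5% Dunnett critical value for two contrasts on 87 df is 2.25 (2.248 before rounding), so the half-width is 2.248 × 0.258 = 0.581 SD. The 5% critical F is 3.10.

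- Ordered pattern, Group I 0.60 SD and Group II 0.30 SD below control: F = n d²/4 = 30 × 0.36 / 4 = 2.70, p = 0.073. The Dunnett intervals are −0.60 ± 0.581 = −1.18 to −0.02 for I-III (p = 0.042) and −0.30 ± 0.581 = −0.88 to 0.28 for II-III. The F-test is not significant while one control contrast is.
- Group I alone 0.557 SD below the other two: F = n d²/3 = 30 × 0.310 / 3 = 3.10, p = 0.050. The Dunnett I-III interval is −0.557 ± 0.581 = −1.14 to 0.02. Here the F-test reaches the 5% level and the contrast does not.

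Neither approach is uniformly more powerful, so the argument rests on estimation.

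**Multiplicity.** Two contrasts in each of three domains make six. At an unadjusted 5% each, the family-wise error would be 1 − 0.95⁶ = 26.5% if they were independent; they are correlated, so this is approximate. On the same basis the three planned F-tests give 1 − 0.95³ = 14.3%.

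**The case against.** The ANOVA is a valid test and matches the plan's wording, which speaks of comparing among groups and nowhere sets the size of a difference from routine as the target. Nor does the plan claim equivalence or say it will read a non-significant F that way. The planned means and SDs, if reported by group with numbers of patients, would let a reader work out crude differences and intervals, and the regression does not exclude group as a term. All of this is correct, and it limits the weight of the point. It does not supply the missing specification: by-group tables, a contrast and an interval are all left to be inferred.

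The two n = 30 examples of conflict sit near the thresholds. In the ordered pattern the methods part only for an observed d between about 0.58 and 0.64 SD, and in the other pattern between about 0.557 and 0.581. In simulation with those patterns as the true means, the two approaches disagreed in about 7% and 16% of trials, in the latter mostly with ANOVA rejecting. This objection stands, and those examples are no argument for Dunnett on power.

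With exactly three groups, unadjusted pairwise tests after a significant F also control family-wise error within a domain, so Dunnett is one valid option and not a necessity.

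Finally, failure, clinical security, perceived security and post-discharge complications are also compared only among the groups, by chi-squared or Fisher's exact test, and lie closer to the stated aim of safety and security. That is fair: it argues for giving control differences there too, not for leaving them out here.

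**Conclusion.** The concern holds. Followed exactly, the plan would deliver one F-test per SATIS-BR domain and would commit to no estimate of how either early-discharge group compares with the named control. This is a weakness in estimation and reporting, not a bias and not an invalid test. Satisfaction is one of several unranked aims, so this is a change that should be made, not a threat to the trial.

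That the F-test cannot identify the group or the direction needs no assumption about sample size. The size of what a null result could conceal does: from ±0.74 SD at 15 per arm to ±0.40 SD at 50 per arm, assuming equal arms and a common SD.

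**What to change.** In the Statistical Analysis Plan, for each SATIS-BR domain:

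- Make the group comparison a linear model with randomised group as factor and Group III as reference. Report the I-III and II-III mean differences on the 1-to-5 scale with 95% confidence intervals. The ANOVA F may stay beside them.
- If significance is to be claimed for the contrasts, use Dunnett intervals within the domain, and state that this does not cover the six contrasts across the three domains.
- Include group as a term in the planned regression on patients' characteristics, leaving that analysis otherwise unchanged. Adjusting the contrasts for a few baseline characteristics fixed in advance is optional and supportive, since the gain is uncertain.

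This needs SAP wording only, with the same data and software. At an assumed 30 per arm, Dunnett intervals are 2.248 / 1.988 = 1.13 times as wide as unadjusted ones (half-width 0.58 against 0.51 SD). Covering all three domains as well, with Dunnett at 5%/3 (critical value 2.68), gives a half-width of 0.69 SD, about 35% wider than unadjusted.

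### Complications are compared only from discharge, so counting starts on day 0 in Group I and day 2 in Group III; with a common end day and analysis as assigned, this works against same-day discharge

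*Combined protocol and SAP*

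**What the plan says.** The Study Protocol and the Statistical Analysis Plan both define three groups by day of discharge: the day of surgery (Group I), the first day after (Group II) and the second day after (Group III, control). For Group III, "the patients will be discharged in the 2nd post-surgery day (routine of Barretos Cancer Hospital").

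The aim that names complications is "the index of post-discharge complications and the costs related to different times of hospitalization". The test that names them is in the Statistical Analysis Plan: "The rates of fail, clinical security, security perception and post-discharge complications will be compared among the groups using chi-squared test", with Fisher's exact test as the alternative. Fail and clinical security are tested in the same sentence, but neither is defined. The aims link the first to the hospital stay: "The specific aims are the evaluation of fail index and factors that influence the permanence in the hospital".

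Two further statements bear on the point. Discharge criteria are named for one group only: "those patients in Group I must match the early hospital discharge criteria defined in the study". The only follow-up day common to all groups is described thus: "At the 10th post-surgery day, in the follow-up, it will be applied the questionnaire SATISBR and an inventory". Neither document states when complication counting ends, describes a count that starts at surgery, or says how Group I patients who fail the criteria are analysed.

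**The concern.** The trial asks whether earlier discharge is safe. In the only comparison that names complications, the assigned group also sets the day on which counting begins. Take a complication between day 1 and day 2. In a Group I patient who has left hospital it is a post-discharge complication. In a Group III patient, still on the ward, the same event is not counted. A difference between the groups could therefore come partly from the endpoint definition and not from the discharge policy. A larger sample would not remove this; it would make the artefact easier to declare significant.

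**Working it through.** The documents contain no complication rate, sample size or power statement, so there is no planned figure to reproduce. What follows illustrates size under stated assumptions.

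**From the documents.** Counting starts on day 0 in Group I and day 2 in Group III. Group II is taken at day 1, as its group definition says (another sentence conflicts with this; see the fix). Significance level 5%, chi-squared test on three groups.

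**Assumed.**
- Counting ends on day 10 in every group, and patients are analysed as assigned.
- The true risk p is identical in all groups: 20%, 10% or 5%.
- Shares s1 and s2 of events fall in days 0-1 and 1-2: (0.10, 0.10), which is even timing over ten days; (0.20, 0.15); and (0.30, 0.20). Together, 20% to 50% of events fall in days 0-2.
- f is the share of Group I's day 0-1 events that precede or block discharge and so are not counted: 0.5 or 1.
- Group size is 100 or 50.

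**Expected counted rates.**
- Group I: p(1 − f·s1)
- Group II: p(1 − s1)
- Group III: p(1 − s1 − s2)

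The I/III ratio is (1 − f·s1)/(1 − s1 − s2), whatever p is.

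| s1, s2 | f = 0.5 | f = 1 |
|---|---|---|
| 0.10, 0.10 | 0.95/0.80 = 1.19 | 0.90/0.80 = 1.12 |
| 0.20, 0.15 | 0.90/0.65 = 1.38 | 0.80/0.65 = 1.23 |
| 0.30, 0.20 | 0.85/0.50 = 1.70 | 0.70/0.50 = 1.40 |

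The reciprocals run from 0.89 to 0.59. Group I would need a true risk 11% to 41% below Group III's to show equal counted rates.

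**Chance of p < 0.05 from the counting rule alone.** This enumerates all three-group outcomes exactly, using Pearson chi-squared with 2 df and no correction. Each range runs from the lowest to the highest early share.

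| True risk, n per group | f = 0.5 | f = 1 | Counted from surgery |
|---|---|---|---|
| 20%, 100 | 7.4% to 23.0% | 6.3% to 12.5% | 5.0% |
| 20%, 50 | 6.1% to 13.2% | 5.6% to 8.4% | 4.9% |
| 10%, 100 | 5.9% to 12.0% | 5.4% to 7.8% | 4.9% |
| 10%, 50 | 5.3% to 8.0% | 5.1% to 6.0% | 4.8% |
| 5%, 100 | 5.1% to 7.6% | 4.9% to 5.7% | 4.6% |
| 5%, 50 | 4.1% to 5.1% | 4.0% to 4.4% | 4.1% |

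With Fisher's exact test the rates are lower in small samples: 4.6% to 7.0% at 10% risk and 50 per group, and 2.4% to 3.2% at 5% and 50.

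**Longer follow-up.** With even timing to day 30, s1 = s2 = 1/30. If every Group I event is counted (f = 0), the ratio is 1/(1 − 2/30) = 1.07, and rejection at 20% risk and 100 per group is 5.4%.

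**Equal windows after discharge.** Suppose each group is followed for ten days from its own discharge and all events in the window count. With constant hazard the I/III ratio is 1.00. If the hazard falls as exp(−kt), the ratio of days 0-10 to days 2-12 is exp(2k): 1.22 at k = 0.1 per day and 2.72 at k = 0.5.

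**The case against.** Four arguments carry weight.

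*The bias is conditional.* A reader might infer that the counted rate must be higher in Group I. The documents do not support that, because they give no end of counting; day 10 is tied only to the questionnaire and an inventory. With equal windows after discharge and constant risk the distortion vanishes. If risk falls after surgery, it stays and keeps the same direction.

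*The discharge criteria work the other way.* If Group I patients who fail them leave the analysis, Group I is selected for lower risk, which could offset the effect. The documents do not say how these patients are analysed. If they are kept but held back for reasons other than a complication, their counting starts later. With an assumed 20% to 40% of Group I staying to day 2, the ratio falls to between 0.6 × 1.125 + 0.4 = 1.07 and 0.8 × 1.70 + 0.2 = 1.56. That weakens the effect without removing it.

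*Complications outside hospital are a legitimate question.* The protocol lists them as an aim, and an event at home or in the support house is not equivalent to one on the ward. It would therefore be too strong to say that the post-discharge comparison tells us nothing about discharge timing. What stands is that it should not be the only complication comparison.

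*The other rates may fill the gap.* Fail or clinical security may cover in-hospital events. Neither is defined, so this can be neither confirmed nor excluded. Even if one of them does, the separately tested post-discharge rate keeps its unequal starts.

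**Conclusion.** The point holds as a conditional flaw in a stated comparison. Groups I and III start counting on different post-operative days by design. Given a common end day and analysis as assigned, identical true risk produces a higher expected counted rate in Group I. Under the assumptions used, the excess ratio is 1.12 to 1.70 and the uncorrected Pearson test rejects in 4% to 23% of trials. Every input to those figures is assumed, so the effect may be negligible or material. The three-group rejection rates also depend on Group II's discharge day; the I/III ratio does not.

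A reader might infer that the plan makes early discharge look falsely safe. The unequal start alone does the reverse: under the stated conditions it makes same-day discharge look worse than it is. Nor do the documents show that in-hospital complications go unrecorded; they show only that no defined comparison includes them. The change should be made: confidence is medium, because the direction is clear only under the stated conditions and the size is unknown.

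**What to change.** Make the main between-group complication comparison any complication from the end of surgery to one fixed post-operative day common to all groups. Day 10 is the only common visit described. Count by assigned group and wherever the event occurs (ward, support house or home), using the hospital chart for in-hospital days and the day-10 visit for the rest. Counting by assigned group also settles how Group I patients who fail the discharge criteria are handled in this comparison.

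Keep post-discharge complications as a secondary measure. State that its starts are unequal across groups and that it should not stand alone as the complication comparison. Define fail and clinical security, and say whether either includes in-hospital complications.

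The cost is wording in both documents, chart abstraction for the in-hospital days and, if the inventory does not already record complications, one added item at day 10. No extra patients or visits are needed.

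Separately, the passages on Group II must be reconciled. The group definition places discharge "on the 1st post-surgery day (Group II"), while a later sentence reads "The patients of Group II will be evaluated in the ambulatory in the 2nd postsurgery day, before the discharge".
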